1.0 STUDY ADMINISTRATIVE INFORMATION AND CLINICAL STUDY PRINCIPLES

1.1 Clinical study principles

This study will be conducted with the highest respect for the individual participants in accordance with the requirements of this clinical study protocol and also in accordance with the following:

- The ethical principles that have their origin in the Declaration of Helsinki.
- Ethical Guideline for Clinical Research (the Ministry of Education, Culture, Sports, Science and Technology and the Ministry of Health, Labour and Welfare, December 22, 2014).
- Good Clinical Practice: Consolidated Guideline (ICH: International Conference on Harmonization of Technical Requirement for Registration on Pharmaceuticals for Human Use. E6)
- All applicable laws and regulations, including, without limitation, data privacy laws and conflict of interest guidelines.

1.2 Clinical study implementation system

This study will be conducted in accordance with the requirements of this clinical study protocol designed and prepared by the sponsor and also in accordance with the following:

Sponsor

Takeda Pharmaceutical Company Limited

Japan Pharma Business Unit

Strategic Medical Research Planning Group, Medical Affairs Department

The sponsor shall be responsible for matters related to planning/preparation, implementation/operation, and results/reporting in this clinical study. Methods of supervision of the contractor entrusted with the services related to this clinical study will be described in the procedure to be prepared separately.

Expenses* required for the operation of this clinical study will be paid by the sponsor.

* : Based on the "Consignment Service Contract," expenses incurred for the services of Office of Clinical Study, monitoring, registration/allocation center, statistical processing, and audit shall

be paid to the contractor entrusted with services related to this clinical study. Expenses agreed by the study site shall be paid to the site based on the "Research Expense Standard."

Chair of the Clinical Study Steering Committee:

PPD

Member of the Clinical Study Steering Committee:

PPD

The chair and member of the Clinical Study Steering Committee shall supervise implementation and reporting of the clinical study, secure medical guidance of a high degree of professionalism and a high-level scientific quality, and revise the study protocol appropriately.

Terms in this protocol are defined as follows:

Study site:

A corporation, governmental agency and sole proprietor conducting the study, excluding cases where only a part of the services related to storage of samples/information, statistical processing and other studies is entrusted.

Collaborative study site:

A study site that conducts collaborative study in accordance with the protocol, including a study site that obtains new samples/information from study subjects and provides other study sites.

Investigators, etc:

Principal investigators and other parties involved in conduction of the study (including operations at institutions involved in collection/distribution of samples/information). Those involved only in providing existing samples/information outside the study sites and those engaged in part of the entrusted operations related to the study are excluded.

Principal Investigator:

2.0 STUDY SUMMARY

Sponsor: Takeda Pharmaceutical Company Limited	Study drug: Omega-3-acid ethyl esters
Study title: Exploratory study of the effects of omega-3-acid ethyl esters on the lipid and lipoprotein profile in the blood	
Protocol number: TAK-085-4002	

Clinical study design:
 
To explore the effects of omega-3-acid ethyl esters on the lipid and lipoprotein profile in the blood in hyperlipidemic patients receiving a hydroxymethylglutaryl-coenzyme A (HMG-CoA) reductase inhibitor in comparison with the control group of patients not treated with omega-3-acid ethyl esters in an unblinded manner by use of high performance liquid chromatography (HPLC) using highly-sensitive gel filtration columns, which is a technique for analyzing lipoprotein.
 
Study subjects who gave consent and were assessed as eligible in the eligibility assessment will be stratified by the factors of “fasting triacylglycerol (TG; < 300 mg/dL or ≥ 300 mg/dL) and age (< 65 years or ≥ 65 years) at the start of the screening period” and allocated to either the group treated with omega-3-acid ethyl esters or the group not treated with omega-3-acid ethyl esters (1:1 ratio).
	

Objectives:
 
To explore the effects of 8-week treatment with omega-3-acid ethyl esters on the lipid and lipoprotein profile in the blood in hyperlipidemic patients receiving a HMG-CoA reductase inhibitor by use of HPLC in comparison with the control group of patients not treated with omega-3-acid ethyl esters.
	
Subjects: Hyperlipidemic patients receiving a HMG-CoA reductase inhibitor	

Planned number of study subjects:
 
50 patients evaluable for the primary endpoint (25 patients in the group treated with omega-3-acid ethyl esters, 25 patients in the group not treated with omega-3-acid ethyl esters)
	
Number of study sites:
 
Around 5 sites

Dose and method of administration:
 
Omega-3-acid ethyl esters 2 g is orally administered immediately after meal twice daily.
	
Route of administration:
 
Oral

Duration of treatment:
 
8 weeks
	
Duration of evaluation:
 
Screening period: 4 weeks

	Treatment period: 8 weeks Total: 12 weeks
Main criteria for inclusion: 
1. Patients diagnosed as hyperlipidemia.2. Patients constantly receiving a HMG-CoA reductase inhibitor at a stable dose for at least 4 weeks at the start of observation period.3. Patients with fasting TG of $150 \leq$ to <400 mg/dL measured at the start of observation period at Visit 1 (Week -4).4. Patients who, in the opinion of the principal investigator or the investigator, are capable of understanding the content of the clinical study and complying with the study protocol requirements.5. Patients who can provide written informed consent prior to the conduction of the clinical study procedures.6. Patients aged ≥ 20 years at the time of informed consent.	
Main criteria for exclusion: 
1. Patients who had clinically significant hemorrhagic disorders (e.g., hemophilia, capillary fragility, gastrointestinal ulcer, urinary tract hemorrhage, hemoptysis, and vitreous hemorrhage) within 24 weeks prior to the start of observation period, or those who concurrently have the above disorders.2. Patients who had thyroid disorders (hyperthyroidism or hypothyroidism) within 24 weeks prior to the start of observation period, those who concurrently have the above disorders, or those who are orally receiving a therapeutic drug for thyroid disorder.3. Patients in whom the type of HMG-CoA reductase inhibitors was changed within 12 weeks prior to the start of observation period.4. Patients who received an eicosapentaenoic acid (EPA) preparation or an EPA/docosahexaenoic acid (DHA) preparation (including supplements) within 12 weeks prior to the start of observation period.5. Patients who started antidyslipidemic agents within 4 weeks prior to the start of observation period.6. Patients with severe hepatic impairment (e.g., Child-Pugh classification C)7. Patients who were previously diagnosed as lipoprotein lipase deficiency or apoprotein C-II deficiency.	

8. Patients who are concurrently having Cushing's syndrome, uremia, systemic lupus erythematosus (SLE), or serum dysproteinemia.
9. Diabetic patients who are currently receiving thiazolidine or insulin.
10. Patients who are concurrently having hypertension of grade III^{Note 1}.
Note 1: Patients with systolic blood pressure of ≥ 180 mm Hg or diastolic blood pressure of ≥ 110 mm Hg regardless of treatment with antihypertensive drugs.
11. Patients who are habitual drinkers drinking an average of over 100 mL per day (expressed in terms of quantity of alcohol), or patients with or with a history of drug abuse or addiction.
12. Pregnant, lactating or postmenopausal women.
13. Patients with a history of hypersensitivity or allergy for omega-3-acid ethyl esters.
14. Patients participating in other clinical studies
15. Patients assessed ineligible in the study by the principal investigator or the investigator

STATISTICAL ANALYSIS METHODS:

(1) Analysis set

Two analysis sets, "Full Analysis Set (FAS)" and "Safety Analysis Set (SAS)" are used in this study.

Define FAS as the population of enrolled study subjects who satisfy the following criterion:

- Study subjects who were randomized and given at least one dose of the study drug.

Define SAS as the population of enrolled study subjects who satisfy the following criterion:

- Study subjects who were given at least one dose of the study drug during this clinical study.

(2) Efficacy analysis

[Primary endpoints]

Change in mean particle sizes of small dense LDL (sdLDL)-C and LDL-C in the specific 20-lipoprotein fraction assay

[Analytical method]

- 1) At each evaluation time point during the treatment period, summary statistics (number of subjects, mean, standard deviation [SD], minimum value, maximum value, quartiles) and a two-sided 95% confidence interval for the mean will be calculated in each treatment group, and a diagram illustrating the change in the mean \pm SD will be prepared.
- 2) At each evaluation time point during the treatment period, percentage of change from baseline will be calculated and analyzed in the same manner as in the above 1).

- 3) At each evaluation time point during the treatment period, study subjects will be stratified by fasting TG and ages at the start of study drug administration, and summary statistics (number of subjects, mean, SD, minimum value, maximum value, quartiles) and a two-sided 95% confidence interval for the mean will be calculated and analyzed in each treatment group.
- 4) At each evaluation time point during the treatment period, percentage of change from baseline will be calculated and analyzed in the same manner as in the above 3).

[Secondary endpoints]

- 1) Change in major lipid constituents in the specific 20-lipoprotein fraction assay
- 2) Change in fatty acids and sdLDL-C in total lipids
- 3) Change in concentration and particle number of lipids, apoprotein and lipoprotein in the blood

[Analytical method]

- 1) At each evaluation time point during the treatment period, summary statistics (number of subjects, mean, SD, minimum value, maximum value, quartiles) and a two-sided 95% confidence interval for the mean will be calculated in each treatment group, and a diagram illustrating the change in the mean \pm SD will be prepared.
- 2) At each evaluation time point during the treatment period, percentage of change from baseline will be calculated and analyzed in the same manner as in the above 1).
- 3) At each evaluation time point during the treatment period, study subjects will be stratified by fasting TG and ages at the start of study drug administration, and summary statistics (number of subjects, mean, SD, minimum value, maximum value, quartiles) and a two-sided 95% confidence interval for the mean will be calculated and analyzed in each treatment group.

(3) Analysis of safety endpoints

[Adverse events]

The following analyses will be performed for each treatment group. Adverse events will be coded using Medical Dictionary for Regulatory Activities (MedDRA) and summarized by System Organ Class (SOC) and Preferred Term (PT).

- Tabulation of frequency of all adverse events
- Tabulation of frequency of adverse events with a causal relationship to the study drug
- Tabulation of frequency of all adverse events by severity
- Tabulation of frequency of adverse events with a causal relationship to the study drug by severity
- Tabulation of frequency of adverse events leading to study drug discontinuation

- Tabulation of frequency of serious adverse events
- Tabulation of frequency of all adverse events by time of onset

Rationale for the number of planned study subjects:

The number of planned study subjects is based on the feasibility to explore the effects of omega-3-acid ethyl esters on the lipid and lipoprotein profile in the blood. The number of planned study subjects is same in the group treated with omega-3-acid ethyl esters and the group not treated with omega-3-acid ethyl esters, which is not based on a statistical consideration.

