6.2 Rationale for the clinical study design

<Rationale>

This clinical study was designed as an open-label study with the control group of patients who will not be treated with omega-3-acid ethyl esters, because the objective is to explore the effects of 8-week, twice-daily, oral treatment with omega-3-acid ethyl esters 2 g on the lipid and lipoprotein profile in the blood in hyperlipidemic patients receiving a HMG-CoA reductase inhibitor. Subjects are to be stratified for allocation (1:1 ratio) by the factors of “fasting TG (< 300 mg/dL or \geq 300 mg/dL) and age (< 65 years or \geq 65 years) at the start of the screening period” that may potentially bias the lipid and lipoprotein profile in the blood, so that the potential bias between the treatment groups is minimized.

<Rationale for the dose regimen>

In accordance with the approved dosage and administration of omega-3-acid ethyl esters, omega-3-acid ethyl esters 2 g is to be orally administered immediately after meal twice daily as the dose regimen in this study. In the Phase 3 confirmatory study in patients with hypertriglyceridemia, superiority of the product 4 g group to the EPA-E group as well as non-inferiority of the product 2 g group to the EPA-E group were confirmed for percentage of change in TG from baseline at the completion of administration of omega-3-acid ethyl esters 2 or 4 g or the control EPA preparation 1.8 g/day. Patients receiving omega-3-acid ethyl esters in actual clinical practice are likely to have increased TG, therefore the dose of 4 g daily was selected as having more marked TG-lowering effect, so that the effects of omega-3-acid ethyl esters on the lipid profiles may be investigated in detail.

<Rationale for the study period>

In the Phase 3 confirmatory study in patients with hypertriglyceridemia, decrease of TG was observed in an early stage (Week 4) after the start of administration with omega-3-acid ethyl

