7.1 Inclusion criteria

Eligibility of study subjects shall be determined in accordance with the following criteria.

1. Patients diagnosed as hyperlipidemia.
2. Patients receiving a HMG-CoA reductase inhibitor continuously at a stable dose regimen for at least 4 weeks at the start of observation period at Visit 1 (Day -29 to Day -1 before the start of study drug administration)
3. Patients with fasting TG of ≥ 150 to < 400 mg/dL at the start of observation period at Visit 1 (Day -29 to Day -1 before the start of study drug administration)
4. Patients who, in the opinion of the principal investigator or the investigator, are capable of understanding the content of the clinical study and complying with the study protocol requirements.
5. Patients who can provide written informed consent prior to the conduction of the clinical study procedures.
6. Patients aged ≥ 20 years at the time of informed consent

[Rationale for the inclusion criteria]

1. These patients were subjected in the clinical study because omega-3-acid ethyl esters is indicated for “hyperlipidemia.”
2. This was set so that the lipid and lipoprotein profile in the blood may be investigated in detail when omega-3-acid ethyl esters is added to a HMG-CoA reductase inhibitor. Change in the dose regimen of the HMG-CoA reductase inhibitor is not allowed during the study, so that efficacy may be assessed accurately.
3. The lower limit was set according to the diagnostic criteria for hypertriglyceridemia in “Japan Atherosclerosis Society (JAS) Guidelines for Prevention of Atherosclerotic Cardiovascular Diseases 2012.” The upper limit was set as using a reference in the clinical settings when adding omega-3-acid ethyl esters to a HMG-CoA reductase inhibitor.
4. 5. These were set as fundamental items for the study.
6. Patients should be ≥ 20 years of age, so that they may make up their mind to participate in the study at their own discretion.

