7 EFFICACY EVALUATIONS

7.1 Primary Endpoint and the Analytical Methods

Analysis Set: Full Analysis Set

Analysis Variables: Change of sd LDL-C by Lipoprotein fraction and particle size of LDL

Time Point : Week 0, Week 4, Week 8

Stratified Variable: Fasting Triglycerides (Week -4)

[Min<= - <300, 300<= - <Max]

Age (Week -4) [Min<= - <65, 65<= - <Max]

Analysis Methods:

- (1) Summary statistics of observed value and 95% confidence interval for the mean will be calculated by treatment groups and time point. In addition, Mean (+/-SD) plots will be made by treatment group and time point. Mean differences and the 95% confidence interval (two-sided) will also be provided.
- (2) The same analyses described in (1) will be performed on percent change from baseline.
- (3) Subgroup analysis of observed value and percent change from baseline will be conducted by stratified variables described above. Summary statistics, 95% confidence interval for the mean, mean differences and the 95% confidence interval (two-sided) will be provided.
- (4) The same analyses described in (3) will be performed on percent change from baseline.

- (5) ANCOVA (analysis of covariance), with Fasting Triglycerides at week -4 (Min ≤ - <300, 300 ≤ - <Max), and Age at week -4 (Min ≤ - <65, 65 ≤ - <Max) as covariate, Treatment group as independent variable, will be applied to the data of percent change at Week 0 to Week 8. (alpha=0.05 through an ANCOVA strategy)

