10.1 Adjustments for Covariates

ANCOVA will be performed on primary and secondary endpoints with Fasting triglycerides at week -4($\text{Min} \leq - < 300$, $300 \leq - \leq \text{Max}$), and Age at week -4($\text{Min} \leq - < 65$, $65 \leq \text{Max}$) as covariate. Details are described in 7.1(5) and 7.2.

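### The SAP's ANCOVA adjusts for screening TG and age only as two-level factors, although both are measured before allocation; continuous terms would be a cheap gain in precision

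*Protocol*

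**What the plan says.** **Allocation.** Protocol 2.0, 6.1 and 6.2 stratify the 1:1 allocation by "fasting triacylglycerol (TG; < 300 mg/dL or ≥ 300 mg/dL) and age (< 65 years or ≥ 65 years", both taken at the start of screening. Section 6.2 describes these as factors "that may potentially bias the lipid and lipoprotein profile in the blood, so that the potential bias between the treatment groups is minimized".

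**Entry range.** Protocol 7.1, item 3, admits "Patients with fasting TG of ≥ 150 to < 400 mg/dL at the start of observation period at Visit 1". No reason for placing the cut at 300 is given.

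**Analysis model.** SAP 7.1(5) specifies "ANCOVA (analysis of covariance), with Fasting Triglycerides at week -4 (Min ≤ - <300, 300 ≤ - <Max), and Age at week -4", with age split at 65, "as covariate, Treatment group as independent variable, will be applied to the data of percent change at Week 0 to Week 8". SAP 10.1 repeats this: "ANCOVA will be performed on primary and secondary endpoints with Fasting triglycerides at week -4", again in two classes. SAP 7.2 carries the same analyses over to the secondary endpoints. This is the only model in the SAP that compares treatments, and it names no other covariate.

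**Data available.** Protocol Appendix A schedules fasting laboratory tests at Visit 1, and date of birth is collected (9.1.2). SAP 6.2.1 tabulates Week -4 TG and age. Both are therefore held as measured values before allocation. The planned size is 25 per group, set on feasibility (Protocol 13.3).

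**The concern.** Protocol 4.1 links rising TG to a shift towards small dense LDL, which is what the primary endpoint measures, and 6.2 treats TG as a possible source of imbalance. With TG in two classes, a patient at 155 mg/dL and one at 295 mg/dL are the same to the model. If the arms differ by chance in where patients lie within a class, the ANCOVA cannot remove that difference, and TG variation within classes stays in the residual. At 25 per arm such differences are not negligible. The stake is a somewhat wider interval for the treatment effect than the collected data allow.

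**Working it through.** The plan states no power, effect size or SD, so there is no figure of its own to reproduce. The check asks how much TG information the cut at 300 keeps and what the loss is worth.

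**Inputs from the documents:** entry TG 150 to <400; cut at 300; 25 per arm; ANCOVA with intercept, treatment, TG class and age class, so 50 - 4 = 46 residual degrees of freedom.

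**Assumed, because the documents are silent:** the TG distribution (log-normal truncated to 150-<400, underlying median 170-250, geometric SD 1.3-1.5; also uniform on the mg/dL scale); the correlation rho between log TG and the outcome; permuted blocks of 4 within strata for the simulation.

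**Step 1. Position of the cut.** (300 - 150)/(400 - 150) = 60% of the way up the range, or ln(2)/ln(400/150) = 71% on the log scale.

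**Step 2. Share of log-TG variance carried by the cut (R²).** The log-normal shapes put 2-26% of patients at 300 or above (about 1-13 of 50), with R² = 18-57%. Uniform TG puts 40% there, with R² of about 66%. The range is 18-66%.

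**Step 3. Chance imbalance left after stratification.** The 95% half-range of the arm difference in mean log TG, in SD units, is 1.96 × √(1 - R²) × √(2/25).
- No stratification (R² = 0): 0.55
- R² = 0.18: 0.50
- R² = 0.57: 0.36
- R² = 0.66: 0.32

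For the log-normal shapes, the edge of this range is a difference of about 9-10% in geometric mean TG. The planned strata do reduce chance imbalance, but they leave part of it.

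**Step 4. Residual variance, two-level against continuous TG.** The ratio is (1 - rho²R²)/(1 - rho²).
- rho = 0.3: R² = 0.66 gives 0.941/0.910 = 1.03; R² = 0.18 gives 0.984/0.910 = 1.08
- rho = 0.5: R² = 0.66 gives 0.835/0.750 = 1.11; R² = 0.18 gives 0.955/0.750 = 1.27

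**Step 5. Simulation of 50-patient stratified trials.** This also counts the cost of estimating terms that allocation does not balance exactly. The entries show how much larger the treatment-effect variance is with two-level terms; a negative entry means the continuous terms do worse.

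| rho | continuous in place of classes | continuous beside classes |
|---|---|---|
| 0 | about -1% to -2% | about -4% to -5% |
| 0.3 | about +2% to +7% | about -1% to +4% |
| 0.5 | about +9% to +26% | about +7% to +21% |

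The formula ratios less the cost at rho = 0 agree closely with these rows.

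**Step 6. Scale, when replacing.** Interval width changes with the square root: √1.02 to √1.07 is 1-3% at rho = 0.3, and √1.09 to √1.26 is 4-12% at rho = 0.5. In patients, 50 × (1 - 1/1.02) to 50 × (1 - 1/1.07) is about 1-3, and 50 × (1 - 1/1.09) to 50 × (1 - 1/1.26) is about 4-10.

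**Step 7. Validity.** In simulation both models were unbiased, with type I error 0.049-0.056.

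**The case against.** The planned model is coherent: it adjusts for the same factors, cut points and time point that drive allocation. That stands, and it is why this is an improvement and not a correction of an error.

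The gain rests on a correlation that the documents do not give. Protocol 4.1 relates TG to LDL quality across patients, whereas the ANCOVA response is each patient's percent change. The correlation could be zero, and it would differ across the nine primary variables in SAP Appendix 1 (five for the sdLDL fraction, four for particle size). That also stands; at zero the continuous terms cost a little.

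Little depends on one model here. The study is exploratory, the SAP also gives unadjusted mean differences with intervals, and the baseline table would show a TG imbalance. This limits the importance of the point, but showing an imbalance does not adjust for it.

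A reader might infer that allocation leaves TG unbalanced, or that 300 is the wrong cut. The documents support neither. Randomisation balances TG within strata in expectation, and Step 3 shows that the strata narrow the chance difference. With uniform TG on the mg/dL scale, the 300 cut captures 0.72 of the variance, against 0.75 for the best two-level split. That TG is right-skewed in these patients, with most below 300, is plausible but is an assumption. Finer strata would leave still smaller cells among 50 patients.

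**Conclusion.** The point holds as a matter of precision. TG and age enter the SAP's only treatment-comparison model in two classes, and under every TG shape tried at least a third of log-TG variance (1 - 0.66 = 34%, up to 82%) lies within classes and is not adjusted for. With continuous terms in place of the classes, the variance gain is about 2-7% at a correlation of 0.3 and 9-26% at 0.5, against a loss of about 1-2% at zero. The size depends on the assumed TG distribution and correlation. A reader might infer from "so that the potential bias between the treatment groups is minimized" that the plan fails its own aim and that the primary result would be biased. It would not be: what remains is chance imbalance and a wider interval, without systematic bias or inflated type I error. This is a cheap improvement.

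**What to change.** Keep the <300/≥300 and <65/≥65 classes for allocation and for the subgroup tables. In SAP 7.1(5), 7.2 and 10.1, enter Week -4 log TG and age as continuous covariates, in one of two ways:

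- **In place of the two-level terms.** The number of parameters is unchanged and the gain is larger, but the randomisation factors leave the model.
- **Beside the two-level terms.** The randomisation factors stay; this uses 2 more of about 46 residual degrees of freedom, and the gain is smaller.

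State the choice before outcome data are analysed, since the study is open-label. The cost is SAP wording: no new data, visits or patients. The downsides are an assumed linear relation with log TG and age, and a small precision loss if TG is unrelated to percent change (about 1-2% when replacing, 4-5% when adding).
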